#### 8.3.3.2 RELATIONSHIP TO STUDY INTERVENTION

To assess relationship of an event to study intervention, the following guidelines are used:

1. Related (Possible, Probable, Definite)
  1. The event is known to occur with the study intervention.
  2. There is a temporal relationship between the intervention and event onset.
  3. The event abates when the intervention is discontinued.
  4. The event reappears upon a re-challenge with the intervention.
2. Not Related (Unlikely, Not Related)
  1. There is no temporal relationship between the intervention and event onset.
  2. An alternate etiology has been established.

---

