*Liver function abnormalities:* We will use a kava product that has removed the potentially liver toxic elements, flavokavain A and B, and has been rigorously tested for quality. However, we will nevertheless closely monitor serum liver biochemistries (AST, ALT, ALP, bilirubin (total, direct, and indirect) and albumin) at baseline, and at weeks 1, 4, 8 and 12. Although the timing of any potential liver toxicity with kava is not known, the timing of the few reported cases in the NIH liver tox database suggests that the onset of symptoms related to hepatotoxicity (including nausea, fatigue) is likely to be between 2 weeks and 12 weeks following initial ingestion. We will also encourage participants to contact the study team for any concerning symptoms that they may have for up to 6 months post-treatment to ensure that no delayed reactions, no matter how unlikely, are missed. We will carefully educate participants about symptoms to watch for throughout the study and following treatment.

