### 3 OBJECTIVES AND ENDPOINTS

OBJECTIVES	ENDPOINTS	JUSTIFICATION FOR ENDPOINTS
Primary		
To evaluate the effect of an 8-week flavokavain A/B-free kava trial in GAD patients on biomarker and anxiety scale changes, and the relationships between these measures, in a double-blind RCT.	
 
Plasma changes in PRKACA, cortisol, urinary TCE, and urinary NA-5HT and cortisol levels
 
Changes in HAM-A score pre to post treatment
 
	
 
Biomarkers of interest
 
Measure of anxiolysis
 

Compliance		
	
 
Liver function tests
 
Number of missed doses
 
	
 
Standard measures of liver function
 
Quantified measure of compliance
 

Tertiary/Exploratory		
N/A	N/A	N/A

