## 6 STUDY INTERVENTION

### 6.1 STUDY INTERVENTION(S) ADMINISTRATION

#### 6.1.1 STUDY INTERVENTION DESCRIPTION

Bottles of flavokavain AB-free kava (75 mg kavalactones/capsule) with the same lot number will be directly purchased from Thorne Research Inc. This product will be used because of its lack of flavokavains A and B (<0.2 mg/capsule) and consistent content of total kavalactones. Participants will take either one 75 mg capsule of kava or one placebo capsule three times a day for one week.

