#### 8.3.4 TIME PERIOD AND FREQUENCY FOR EVENT ASSESSMENT AND FOLLOW-UP

Unanticipated problems will be recorded in the data collection system throughout the study.

The PI will record all reportable events with start dates occurring any time after informed consent is obtained until 7 (for non-serious AEs) or 30 days (for SAEs) after the last day of study participation. At

each study visit, the investigator will inquire about the occurrence of AE/SAEs since the last visit. Events will be followed for outcome information until resolution or stabilization.

---

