### 8.3.6 SERIOUS ADVERSE EVENT REPORTING

SAEs that are unanticipated, serious, and possibly related to the study intervention will be reported to the Independent Monitors(s), IRB, FDA, and NCCIH in accordance with requirements. For the IND:

- 7-day IND Safety Report (unexpected fatal or life-threatening AEs related to the intervention); a copy of the report sent to the FDA will be submitted to the NCCIH Program Officer and Independent Safety Monitor(s) within 24 hours of FDA notification.
- 15-day IND Safety Report (any other serious and unexpected AE related to the intervention); a copy of the report submitted to the FDA will be submitted to the NCCIH Program Officer and Independent Safety Monitor(s) within 24 hours of FDA notification.

All other AEs documented during the course of the trial will be reported to NCCIH on an annual basis by way of inclusion in the annual report and in the annual AE summary which will be provided to NCCIH and to the Independent Monitors. The Independent Safety Monitor(s) Report will state that all AEs have been reviewed

---

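### Participants are asked to report symptoms for six months after treatment, but the recording rule closes 7 or 30 days after participation ends

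*Combined protocol and SAP*

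**What the plan says.** - **Dosing.** Section 6.1.1 gives "one 75 mg capsule of kava or one placebo capsule three times a day for one week".
- **Expected onset.** In section 2.3.3, under liver function abnormalities, the onset of symptoms of hepatotoxicity "is likely to be between 2 weeks and 12 weeks following initial ingestion".
- **Solicited reports.** The same paragraph encourages participants to contact the team about concerning symptoms "for up to 6 months post-treatment to ensure that no delayed reactions, no matter how unlikely, are missed".
- **Recording rule.** Section 8.3.4 has the investigator record events by start date, from consent "until 7 (for non-serious AEs) or 30 days (for SAEs) after the last day of study participation".
- **Causality.** Section 8.3.3.2 lists four guidelines under Related, a class that includes Possible. The third is "The event abates when the intervention is discontinued" and the fourth is recurrence on re-challenge. The first guideline under Not Related is "There is no temporal relationship between the intervention and event onset". The section does not say how many guidelines must be met or what interval counts as a temporal relationship.

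**The concern.** The two safety sections set different horizons. Section 2.3.3 invites reports for six months, with the stated aim of missing no delayed reaction. Section 8.3.4 gives those reports a recording rule for only part of that time. A participant who follows the instruction and calls in month five about symptoms that have just begun describes an event that the plan does not require anyone to enter in the data. Delayed liver toxicity is the reason the synopsis gives for following participants after treatment. With 26 randomized participants, a single hepatic case could change the safety conclusion.

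The causality guidelines raise a related but smaller question. If onset is expected after dosing has stopped, a guideline about what happens on stopping has nothing to work with, and the assessor is left with an undefined notion of timing.

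**Working it through.** The plan states no figure to reproduce. The check is a day count.

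**Inputs**
- First dose on Day 1 and last dose about Day 7 (section 6.1.1, one week).
- Onset window of 2 to 12 weeks after first ingestion, taken as Day 14 to Day 84 (section 2.3.3).
- Final visit on Day 84 ± 1 (Schedule of Activities). The synopsis gives 13 weeks of participation, which is Day 91.
- Recording margin of 7 days for non-serious and 30 days for serious events (section 8.3.4).
- Contact period of 6 months post-treatment (section 2.3.3). Assumption: 6 months is 182 days, so it ends on Day 7 + 182 = Day 189. With 183 days it ends on Day 190 and each gap grows by one day.

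**Recording gap for a completer**

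Recording end = last day of participation + margin. Gap = 189 − recording end.

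| Last day of participation | Event type | Recording ends | Gap | Share of 182-day contact period |
|---|---|---|---|---|
| Day 84 | non-serious | 84 + 7 = 91 | 189 − 91 = 98 days | 98/182 = 54% |
| Day 84 | serious | 84 + 30 = 114 | 189 − 114 = 75 days | 75/182 = 41% |
| Day 91 | non-serious | 91 + 7 = 98 | 189 − 98 = 91 days | 91/182 = 50% |
| Day 91 | serious | 91 + 30 = 121 | 189 − 121 = 68 days | 68/182 = 37% |

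The rule works on start dates. An event that began on Day 80 and was reported on Day 150 is inside it. The gap concerns events that begin after the recording end.

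**Is the onset window covered?** The earliest recording end in the table, Day 91, falls after Day 84. Days 14 to 84 are therefore fully covered for anyone who stays to the final visit.

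**Early withdrawal.** Section 7.2 stops all study activity at withdrawal. If that ends participation on Day 7, recording ends on Day 14 (7 + 7) or Day 37 (7 + 30). That covers 1 of the 71 days from Day 14 to Day 84 (1%) for non-serious events, or 24 of 71 (34%) for serious events. The plan expects 26 − 20 = 6 participants not to complete and does not say when they leave.

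**Causality guidelines.** Onset on Days 14 to 84 is 14 − 7 = 7 to 84 − 7 = 77 days after the last dose, so the whole expected window lies after treatment. Abatement on stopping cannot be observed for such an event, and the design contains no re-challenge. The other two guidelines can still be met: section 2.3.1 lists rare liver toxicity as a known risk, and section 2.3.3 supplies a latency that makes a Week 8 onset plausible in time.

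**The case against.** A reader might infer three stronger things, and the documents support none of them.

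1. **That the recording window misses the expected onset period.** It does not for completers. Section 8.3.4 counts from the last day of participation, not from the last dose, and the gap opens only after Day 84.
2. **That the causality list pushes late liver cases into Not Related.** Section 8.3.3.2 offers guidelines, places Possible under Related, and leaves two guidelines that a late case can meet. Requiring all four would make every event unrelated, because no re-challenge is planned for anyone; that reading is implausible. A classification of unrelated is left open, not required.
3. **That relatedness alone decides whether a serious event reaches the monitors promptly.** Section 8.3.6 does say "SAEs that are unanticipated, serious, and possibly related to the study intervention will be reported". But section 10.1.6 has the DSMB review any reported serious event within 48 hours and sends serious, unexpected events onward without a relatedness test. Under section 2.3.3 a hepatologist reads the liver results blinded and passes all adverse events to the DSMB, and section 10.1.7 sends liver function to the independent monitor. Section 8.3.6 also requires the event to be unanticipated, and section 2.3.1 already names acute liver injury as a potential risk, so expectedness may govern expedited reporting whatever the causality call.

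It can also be said that the metabolic panel at Weeks 1, 4, 8 and 12 detects enzyme rises however they are labelled, that recorded events are followed to resolution or stabilization, that section 8.3.4 records unanticipated problems throughout the study, and that nothing forbids staff from noting a late call. All of this stands. It does not close the gap: the scheduled panels end at Week 12, an unanticipated problem is a narrower category than a delayed reaction, and permission to note a call is not a rule to record it.

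**Conclusion.** The conflict between sections 2.3.3 and 8.3.4 is real. For a completer, about 98 days (non-serious) or 75 days (serious) of the period in which reports are solicited fall outside the recording rule, or 91 and 68 days if participation runs to Day 91. This is a gap beyond the expected onset window, not within it, so it concerns the unlikely late case that section 2.3.3 says it wants to catch. The causality point is a secondary clarification.

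The figures assume one week of dosing, 182 days for six months, and participation that ends at the final visit. Two inconsistencies bear on them and need reconciling in their own right. The objectives table in section 3 reads "To evaluate the effect of an 8-week flavokavain A/B-free kava trial in GAD patients", while the operational sections give one week; with eight weeks of dosing, part of the onset window would fall on treatment. The Schedule of Activities ends on Day 84, which is 11 weeks after Day 7, while the synopsis promises 12 weeks after the end of treatment. The second inconsistency only moves the gap between the two pairs of values above.

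**What to change.** **Section 8.3.4.** Extend the recording window for participant-reported hepatic events and for serious adverse events to the 6 months in section 2.3.3, or otherwise reconcile the two sections so that every report the trial solicits has a stated recording rule. State at the same time what the last day of study participation means for someone who withdraws.

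**Section 8.3.3.2.** Note that the abatement and re-challenge guidelines cannot inform an event that starts after dosing has ended, and that temporal relationship is to be read against the protocol's own 2 to 12 week onset window, so that a late liver event is not classed as unrelated on timing alone. A default of possibly related would be one convention among several and is not needed for this.

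**Cost.** A wording amendment and a longer recording period, to about Day 189 for the events named. No new visits are needed, because late events are reported by participants.

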#### 8.3.3.3 EXPECTEDNESS

The Study PI and Independent Monitoring Committee will be responsible for determining whether an SAE is expected or unexpected. An adverse event will be considered unexpected if the nature, severity, or frequency of the event is not consistent with the risk information previously described for the intervention.

---

#### 8.3.4 TIME PERIOD AND FREQUENCY FOR EVENT ASSESSMENT AND FOLLOW-UP

Unanticipated problems will be recorded in the data collection system throughout the study.

The PI will record all reportable events with start dates occurring any time after informed consent is obtained until 7 (for non-serious AEs) or 30 days (for SAEs) after the last day of study participation. At

each study visit, the investigator will inquire about the occurrence of AE/SAEs since the last visit. Events will be followed for outcome information until resolution or stabilization.

---

### 8.3.5 ADVERSE EVENT REPORTING

AEs documented during the course of the trial will be reported to NCCIH on an annual basis by way of inclusion in the annual report and in the annual AE summary which will be provided to NCCIH and to the Independent Monitors. The Independent Safety Monitor(s) Report will state that all AEs have been reviewed.

---

### 8.3.6 SERIOUS ADVERSE EVENT REPORTING

SAEs that are unanticipated, serious, and possibly related to the study intervention will be reported to the Independent Monitors(s), IRB, FDA, and NCCIH in accordance with requirements. For the IND:

- 7-day IND Safety Report (unexpected fatal or life-threatening AEs related to the intervention); a copy of the report sent to the FDA will be submitted to the NCCIH Program Officer and Independent Safety Monitor(s) within 24 hours of FDA notification.
- 15-day IND Safety Report (any other serious and unexpected AE related to the intervention); a copy of the report submitted to the FDA will be submitted to the NCCIH Program Officer and Independent Safety Monitor(s) within 24 hours of FDA notification.

All other AEs documented during the course of the trial will be reported to NCCIH on an annual basis by way of inclusion in the annual report and in the annual AE summary which will be provided to NCCIH and to the Independent Monitors. The Independent Safety Monitor(s) Report will state that all AEs have been reviewed

---

### 8.3.7 REPORTING EVENTS TO PARTICIPANTS

In the case of abnormal lab values (liver functions), the PI will address these findings with the study subjects and provide the subject with a copy of the result for their current physician.

---

### 8.3.8 EVENTS OF SPECIAL INTEREST

None

---

### 8.3.9 REPORTING OF PREGNANCY

All individuals of child bearing age range will be required to provide a urine sample for pregnancy testing at the screening visit. If they are determined to be pregnant they will be excluded from the study.

## 8.4 UNANTICIPATED PROBLEMS

### 8.4.1 DEFINITION OF UNANTICIPATED PROBLEMS (UP)

The Office for Human Research Protections (OHRP) considers unanticipated problems involving risks to subjects or others to include, in general, any incident, experience, or outcome that meets **all** of the following criteria:

- Unexpected in terms of nature, severity, or frequency given (a) the research procedures that are described in the protocol-related documents, such as the IRB-approved research protocol and informed consent document; and (b) the characteristics of the subject population being studied;
- Related or possibly related to participation in the research (“possibly related” means there is a reasonable possibility that the incident, experience, or outcome may have been caused by the procedures involved in the research); and
- Suggests that the research places subjects or others at a greater risk of harm (including physical, psychological, economic, or social harm) than was previously known or recognized.

### 8.4.2 UNANTICIPATED PROBLEM REPORTING

Incidents or events that meet the OHRP criteria for unanticipated problems require the creation and completion of an unanticipated problem report form. OHRP recommends that investigators include the following information when reporting an adverse event, or any other incident, experience, or outcome as an unanticipated problem to the IRB:

- Appropriate identifying information for the research protocol, such as the title, investigator’s name, and the IRB project number;
- A detailed description of the adverse event, incident, experience, or outcome;
- An explanation of the basis for determining that the adverse event, incident, experience, or outcome represents an unanticipated problem;
- A description of any changes to the protocol or other corrective actions that have been taken or are proposed in response to the unanticipated problem.

To satisfy the requirement for prompt reporting, unanticipated problems will be reported using the following timeline:

- Unanticipated problems that are serious adverse events will be reported to the IRB, Independent Safety Monitor(s), and NCCIH within 7 days of the investigator becoming aware of the event.
- Any other unanticipated problem will be reported to the IRB, Independent Safety Monitor(s), and NCCIH within 14 days of the investigator becoming aware of the problem.

All unanticipated problems should be reported to appropriate institutional officials (as required by an institution's written reporting procedures), the supporting agency head (or designee), and OHRP within one month of the IRB's receipt of the report of the problem from the investigator.

---

#### 8.4.3 REPORTING UNANTICIPATED PROBLEMS TO PARTICIPANTS

During this study we will follow the NIH and UF IRB guidelines on reporting unanticipated problems to study participants.

## 9 STATISTICAL CONSIDERATIONS

### 9.1 STATISTICAL HYPOTHESES

- Primary Efficacy Endpoint(s):
  - Mean PRKACA reduction will be 30% higher in kava group than placebo group
  - Mean PRKACA and HAM-A score reductions in placebo group will be correlated by at least 0.3
- Secondary Efficacy Endpoint(s):
  - Measurable DHM levels will be detected in 8/10 participants in kava arm

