## 1 PROTOCOL SUMMARY

### 1.1 SYNOPSIS

- Title:** A Phased Clinical Trial of a Dietary Supplement Kava: Biomarker Changes and Anxiolytic Effects
- Study Description:** This study will examine the utility of plasma and urinary based biomarkers for the anxiolytic properties of kava, a natural dietary supplement. We will conduct a one week, double blind, randomized placebo controlled trial of kava, dosed at three 75 mg capsules per day, vs placebo, in adults with generalized anxiety disorder. Clinical measures of anxiety, blood, and urine will be obtained. Biomarkers of interest include PRKACA, cortisol, urinary TCE, and NA-5HT. CYP2D6 testing will be conducted at the screening visit to examine, at the end of the study, whether kava metabolism through this enzyme affects the biomarker responses. Participants will be assessed pre- and post-treatment. They will also be followed for 12 weeks after the end of treatment to identify any potential rare adverse events, particularly liver toxicity, that appear in a delayed fashion.
- Objectives:** Primary Objective: To evaluate the effect of a one week flavokavain A/B-free kava trial in GAD patients on biomarker and anxiety scale changes, and the relationships between these measures, in a double-blind RCT.
- Endpoints:** Primary Endpoint: Plasma PRKACA, cortisol, urinary TCE, urinary NA-5HT and cortisol levels  
Secondary Endpoints: Compliance determined by missed doses and increased dihydromyricetin (DHM) levels
- Study Population:** We will screen 30 subjects in order to randomize 26 adults with GAD ages 18-50 for entry into the study, with at least 20 of them completing the study. There are no restrictions on ethnicity, social background, or gender. Subjects will only be accepted into the study if they are free of any history of significant medical illness as determined by history taking, physical examination, and routine laboratory tests. Female subjects of child-bearing potential will be given a pregnancy test.

**Phase:** 2

**Description of Sites/Facilities** The University of Florida Clinical Research Center will be used to enroll participants and conduct research procedures. This facility is designed for clinical research.

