## 2 INTRODUCTION

### 2.1 STUDY RATIONALE

To validate PRKACA reduction (primary outcome), cortisol, urinary TCE, and NA-5HT reductions (secondary outcomes) as biomarkers for kava-induced anxiolysis in GAD.

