## 4 STUDY DESIGN

### 4.1 OVERALL DESIGN

**Aim:** To validate PRKACA reduction (primary outcome), cortisol, urinary TCE, and NA-5HT reductions (secondary outcomes) as biomarkers for kava-induced anxiolysis in GAD.

**Study design:** We will recruit and screen potential participants until we are able to randomize and enroll 26 individuals with GAD, with the expectation that 20 will complete the study (10 per arm) based on a conservative estimate of a 25% drop-out rate (the drop-out rate for our pilot study was 19%). We will build on our prior work with smokers by evaluating the utility of PRKACA as a biomarker for kava-induced anxiolysis among individuals with GAD. A one week double-blinded randomized, parallel, placebo-controlled trial of kava in GAD patients will be conducted. To minimize the risk of adverse events, particularly liver dysfunction, we will use flavokavain A/B-free kava in this study. Participants will be randomized, stratified by sex, to one of two conditions—placebo dosed three times a day or 75 mg of kava dosed three times a day. All pills will be taken with meals. Potential adverse effects will be evaluated via serum liver biochemistries and assessment of clinical symptoms in all participants at baseline, post treatment (day 7) and every 4 weeks for 12 weeks following discontinuation of treatment. Blood and urine for biomarker assessments will be collected at baseline and post treatment (day 7). CYP2D6 testing will be conducted at the screening visit to examine, at the end of the study, whether kava metabolism through this enzyme affects the biomarker responses.

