### 9.2 SAMPLE SIZE DETERMINATION

We will recruit and screen potential participants until we are able to randomize and enroll 26 individuals with GAD, with the expectation that 20 will complete the study (10 per arm) based on a 75% success rate (the retention rate for our pilot study was 81%). Of particular interest is determining the utility of measuring changes in PRKACA as a marker of kava-induced anxiolysis. To provide context, the effect size seen in our pilot work was .794 (Cohen's  $f$ ) for PRKACA reductions on kava from baseline. Based on the proposed design, with 10 subjects per arm, we have 0.80 power to detect an effect size (Cohen's  $f$ ) of 0.73 (82, 83). While this represents a large effect size, it is consistent with what was found in our pilot work.

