### 9.4 STATISTICAL ANALYSES

#### 9.4.1 GENERAL APPROACH

In this aim, we will explore the effect of kava supplement on changes in PRKACA, cortisol, urinary TCE, and NA-5HT. Separate 2 x 2 (Condition (Placebo / Kava) x Time (Baseline and Post-treatment, within condition) generalized linear mixed models (GLMM) will be analyzed for (a) PRKACA, (b) cortisol, urinary TCE, and NA-5HT outcomes. Of primary interest is exploring effect sizes for the interaction effect (difference in slopes) for those outcomes over weeks 0 (baseline) to 1 under placebo and kava conditions. Simple main effects will provide information about the within-subjects slope for each condition. GLMM analyses allow for missing data for an intent-to-treat approach, and can accommodate measurement of study subjects at different time points during the study, incorporate time varying covariates, flexible covariance structures, and a variety of dependent variable distributions (including counts and dichotomous) (85, 86). The statistical model will contain main effects for condition and time and the condition by time interaction. Of primary interest is the treatment by time interaction effect, as that will reflect the effect of the kava intervention.

---

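### The only PRKACA–HAM-A correlation hypothesis, labelled primary, is set in the placebo group although the aim concerns kava-induced anxiolysis, and section 9.4 has no HAM-A model or correlation method

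*Combined protocol and SAP*

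**What the plan says.** **Aim.** Section 2.1 gives the rationale as "To validate PRKACA reduction (primary outcome), cortisol, urinary TCE, and NA-5HT reductions (secondary outcomes) as biomarkers for kava-induced anxiolysis in GAD". Section 4.1 repeats it ("as biomarkers for kava-induced anxiolysis in GAD"), and section 9.2 adds: "Of particular interest is determining the utility of measuring changes in PRKACA as a marker of kava-induced anxiolysis".

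**Objective and endpoints.** The primary objective in section 3 concerns "biomarker and anxiety scale changes, and the relationships between these measures, in a double-blind RCT", and section 1.1 has the same objective apart from the treatment length. The Primary row of section 3 also lists "Changes in HAM-A score pre to post treatment". The primary endpoint in the section 1.1 synopsis is "Plasma PRKACA, cortisol, urinary TCE, urinary NA-5HT and cortisol levels", without HAM-A.

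**Hypotheses.** Section 9.1 has two entries under primary efficacy endpoints. One is a PRKACA reduction 30% higher on kava than on placebo. The other is "Mean PRKACA and HAM-A score reductions in placebo group will be correlated by at least 0.3".

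**Analysis.** In section 9.4.1, separate condition-by-time mixed models "will be analyzed for (a) PRKACA, (b) cortisol, urinary TCE, and NA-5HT outcomes". Section 9.4.2 refers back to that text, 9.4.3 says no analysis is needed for the secondary endpoint, and 9.4.9 is marked not applicable. Within 9.4, HAM-A appears only among the baseline descriptives in 9.4.5.

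**The concern.** The hypothesis that should link the biomarker to anxiety relief sits in the arm that receives no kava. Followed as written, the trial would report a primary relationship result that is judged without any participant on kava, and that result could not speak to kava-induced anxiolysis.

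Two gaps make this harder to repair at the analysis stage. The correlation has no named coefficient, analysis set or interval. HAM-A change has no outcome model, so the plan does not say how the trial will estimate whether kava lowered anxiety at all. The wording also refers to mean reductions. Within one arm there is one mean per measure, so there is nothing to correlate until the text says individual changes.

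**Working it through.** **1. Which group each passage refers to**

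| Section | Content | Group |
|---|---|---|
| 2.1, 4.1, 9.2 | PRKACA as a marker of kava-induced anxiolysis | people taking kava |
| 1.1, 3 | relationships between biomarker and anxiety changes | the trial; no arm named |
| 9.1, first primary hypothesis | PRKACA reduction | kava versus placebo |
| 9.1, second primary hypothesis | PRKACA–HAM-A correlation of at least 0.3 | placebo only |
| 9.4.1 to 9.4.3, 9.4.9 | no correlation analysis; no HAM-A outcome | none |

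The only entry that concerns the relationship names placebo. No other section supplies a kava-arm or pooled version.

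**2. Whether the data exist.** The schedule in section 1.3 has biomarkers at Day 1 and Week 1, and HAM-A once before treatment and again at Week 1. Both changes can be computed in both arms. The timing of the pre-treatment HAM-A is unclear: section 1.3 marks it under Phone Screen, section 5.1 requires the score at screening, and the screening list in section 1.2 omits it.

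**3. What a value of 0.3 would mean at this sample size.** The documents give no power or precision for the correlation, so there is no plan figure to reproduce. The 0.80 power at Cohen's f = 0.73 in section 9.2 concerns PRKACA and is not used here.

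Inputs: 10 completers per arm (sections 4.1 and 9.2); 26 / 2 = 13 per arm if everyone completes. Assumptions: bivariate normal changes, a 95% level (no alpha is stated), and, for the chance rate only, 0.3 read as a cut-off on the observed correlation (no decision rule is stated).

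*Chance rate with no true correlation:* t = r√(n−2) / √(1−r²), on n−2 degrees of freedom.
- n = 10: t = 0.3 × √8 / √0.91 = 0.889; P(t on 8 df ≥ 0.889) = 0.200.
- n = 13: t = 0.3 × √11 / √0.91 = 1.043; P(t on 11 df ≥ 1.043) = 0.160.

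*95% CI at an observed 0.30:* tanh[atanh(0.30) ± 1.96/√(n−3)], with atanh(0.30) = 0.3095.
- n = 10: 0.3095 ± 1.96 × 0.3780 = −0.431 to 1.050, so r from −0.41 to 0.78.
- n = 13: 0.3095 ± 1.96 × 0.3162 = −0.310 to 0.929, so r from −0.30 to 0.73.

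*Spearman, n = 10:* chance rate 0.193 over all permutations. With SE √((1 + 0.30²/2)/7) = 0.386, the CI is −0.42 to 0.79.

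These figures are the same for either arm. They measure how little a value of 0.3 shows at this size; they do not measure the effect of naming the wrong arm.

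**The case against.** **It may be a one-word slip.** That is plausible, since no kava-arm hypothesis appears anywhere. The documents do not settle it. If it is a slip, the primary hypothesis still needs correcting; if it is deliberate, the analysis that the aim needs is missing. In both cases the method and the HAM-A model remain absent.

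**The plan is exploratory.** Section 4.2 frames PRKACA as a potential marker to be explored, and section 9.4.1 speaks of exploring effect sizes. This stands, and it means that the language of validation in 2.1 and 4.1 is not the whole plan. It does not explain why the relationship is placed in the placebo arm under a primary label.

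**A kava-only correlation narrows the objective.** The objective names no arm and covers several biomarkers, and a kava-arm value alone does not separate kava response from placebo response. This stands, and is the reason to show the placebo value beside it. Pooling gives more precision (n = 20: tanh[0.3095 ± 1.96/√17] = −0.16 to 0.66), but a pooled correlation answers a somewhat different question.

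**Stronger readings that the documents do not support.**
- A reader might infer that the trial passes or fails on an observed correlation of 0.3. Section 9.1 states a hypothesis and no section gives a decision rule.
- A reader might want to quantify how often the placebo and kava arms would disagree. That needs true correlations which the documents do not give, and two kava arms of 10 would also often disagree through noise alone.
- A reader might infer that the arm can be picked after the data are seen. Section 9.1 fixes it as placebo. Only the coefficient is open. In simulated bivariate normal samples of 10 with no true correlation, Pearson or Spearman reaches 0.3 about 24% of the time, against 20% for Pearson alone.

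**Conclusion.** Wrong as written. The arm named in section 9.1 contradicts the stated aim, and section 9.4 cannot carry out the relationship part of the primary objective or analyse HAM-A change. This rests on the text alone and needs no assumption about the true correlation.

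The scope is limited. The kava-versus-placebo PRKACA hypothesis and its model are unaffected, and no data are lost. A reader might infer that moving the hypothesis to the kava arm would let the trial validate PRKACA. It would not: under the assumptions listed in the working, the 20% chance rate and the interval from −0.41 to 0.78 apply equally to a kava arm of 10 (16%, and −0.30 to 0.73, with 13). At this size the correlation can only be estimated.

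**What to change.** Before unblinding:

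1. **Section 9.1.** Correct the arm, or justify placebo. In either case pre-specify the kava-arm correlation of individual PRKACA change with individual HAM-A change, in participants with both changes observed. Remove the reference to means. Name one coefficient, for example Spearman. Report the estimate with its 95% CI and the placebo-arm value alongside for comparison. Do not use 0.3 as a pass mark.
2. **Sections 2.1 and 4.1.** Align the language of validation with the exploratory wording already in 4.2 and 9.4.1.
3. **Section 9.4.1.** Add HAM-A as an outcome in the same condition-by-time model, using the one pre-treatment HAM-A that is collected. Reconcile sections 1.2, 1.3 and 5.1 on when it is taken.
4. **Sections 1.1, 3 and 9.1.** State consistently whether HAM-A change is a primary endpoint.

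The cost is protocol and SAP wording, with no added participants, visits or assessments. The downside is a weaker stated claim, an estimate in place of validation, and a kava-arm estimate that stays imprecise.
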